### **Sedentary behaviour and physical activity**

Daily activity levels are measured using the activPAL3™ physical activity monitor (PAL Technologies, Glasgow, UK). The activPAL3 is a small (53 × 35 × 7 mm), lightweight (15 g) triaxial accelerometer that records movement in the vertical, anteroposterior and mediolateral axes, and also determines posture (sitting or lying, standing and stepping) based on acceleration information.

The device will be attached directly to the skin on the front of the right thigh with transparent, waterproof, 3M Tegaderm™ tape and the use of a nitrile sleeve.

Participants will be asked to wear the accelerometer for 8 consecutive days, without removing it at any time. Data will be uploaded using the activPAL software and processed using customised software written in MATLAB R2013b (MathWorks, Natick, MA, USA).

The total amount of sedentary time is based on the sedentary posture (sitting or lying), and calculated as the mean time spent in a sedentary position during waking time per day. The method used to determine waking time has been described elsewhere (38).

The total amount of standing time was based on the standing posture, and calculated as the mean time spent standing during waking time per day. The total amount of stepping is based on the stepping posture, and calculated as the mean time stepping during waking time per day. Stepping time (physical activity) is further classified into higher intensity physical activity (HPA; minutes with a step frequency >110 steps/min during waking time) and lower intensity physical activity (LPA; minutes with a step frequency ≤110 steps/min during waking time) (39).

### **Metabolic outcomes**

#### **Venous blood sampling:**

Blood withdrawal will take place, according to standard hospital operating procedures, via the insertion of a cannula into a proximal vein of the non-dominant arm. In total 8 collecting tubes will be collected (total blood volume of 40 mL) for (standard) laboratory assessments (please see above). Any remainders of the blood samples after quantification of the primary laboratory values will be stored in a biobank for future determination of (bio)markers that might be associated with physical activity.

There are no specific risks associated with blood withdrawal except for bruising or vasovagal collapse as a reaction to the sharp sting whilst penetrating the skin. In case of collapse the study physician on call will be alerted and appropriate action will be undertaken.

As a safety measure the fasting circulating level of glucose is assessed on site with the use of Lifescan One Touch Verio glucose meter to identify those with low (< 3.8 mmol/L) or high fasting glucose levels (> 15 mmol/L). Low or high fasting glucose levels will be brought to the

attention of the internist on call who will take any necessary step according to good clinical practice guidelines (if necessary bring the participant either into immediate care or notify the very same day the participant's General Practitioner).

### **Body composition:**

Weight and height will be measured without shoes and wearing light clothing only using a scale and stadiometer to the nearest 0.5 kg or 0.1 cm (Seca, Hamburg, Germany). Waist circumference will be measured with a flexible plastic tape measure (Seca, Hamburg, Germany), in duplicate midway between the lower rib margin and the iliac crest at the end of expiration, to the nearest 0.5 cm. In addition, body composition will be assessed non-invasively using bio-electric impedance spectroscopy (BIS: model 4200; Xitron Technologies, San Diego, California). This procedure will be executed with the use of two handgrips through which a low-voltage current will run and the computed electrical resistance determines fat free mass. There are no known risks to this procedure.

### **Quality of life:**

Health related quality of life will be measured with the SF-36 and EQ-5D, the most widely used generic preference-based health status measures. The EQ-5D is a short questionnaire that covers five dimensions of health: Mobility, Self-Care, Usual Activities, Pain/Discomfort and Anxiety/Depression. The SF-36 is a generic and easily self-administered quality of life instrument.

### **Depressive symptoms:**

Depressive symptoms will be assessed by a validated Dutch version of the 9-item Patient Health Questionnaire (PHQ-9) (40). The PHQ-9 is a self-administered questionnaire based on the DMS-IV (Diagnostic and Statistical Manual of Mental Disorders, Fourth Edition) criteria for a major depressive disorder. It comprises nine items rated on a 4-point scale, ranging from 0 = "not at all" to 3 = "nearly every day". Response options can generate a continuous score ranging from 0 (no symptoms) to 27 (all symptoms present nearly every day); scores 10–14 represent moderate and 15–27 moderately severe to severe depression symptoms. The PHQ-9 scale will also be used as a dichotomous variable with a pre-defined cut-off level of 10, which represents the presence of clinically relevant depressive symptoms.

### **Physical function:**

Timed-chair stand test will be carried out as a measure of physical performance. The time taken to rise from a sitting to a standing position with straight back and legs, and then sit

down again 10 times as fast as possible was measured using a stopwatch. The times recorded were used to calculate chair rise speed.

Handgrip strength (kg) will be measured with hand-held dynamometer, three maximum force trials with each hand.

### **Withdrawal of individual subjects**

Subjects can leave the study at any time for any reason if they wish to do so without any consequences with regard to their medical treatment in general or any treatment at all at the Maastricht UMC+. The investigator can decide to withdraw a subject from the study for urgent medical reasons. Reasons for withdrawal of drop-out will be logged.

#### **6.3.1 Specific criteria for withdrawal (if applicable)**

If during the inclusion visit a severe carotid atherosclerotic plaque is discovered in the region of interest the participant will be withdrawn from the trial.

If during the duration of the trial any cardiovascular events occurs participants will be withdrawn from the trial.

If participation in the trial leads to uncontrollable hypo- or hyperglycaemia participants will be withdrawn from the trial.

If any other serious medical condition arises during the trial which requires medical specialty treatment or hospitalisation, participants will be withdrawn from the trial.

#### **6.4 Replacement of individual subjects after withdrawal**

Participants will not be replaced.

#### **6.5 Follow-up of subjects withdrawn from treatment**

Any participants withdrawn from the trial will be followed up by questionnaire to be able to determine, also in retrospect, whether their withdrawal might have been due to any medical condition which occurred as a consequence of participation in the trial. If such is suspected the participant will be asked to consent to contact his or her general practitioner for further information. This questionnaire specifically bears the option: "I do not wish to be contacted any further by the LiPAT and do not grant permission to contact my general practitioner".

### **6.6 Premature termination of the study**

It is not to be expected that LiPAT will be terminated prematurely. In principle because the level of exercise intensity does not exceed the participants individual level of exercise intensity (e.g., we do not suggest that the participants start running / jogging etc.). We do suggest that the participant actively diminishes his or her sedentary behaviour in a fashion he or she thinks appropriate (e.g., by going for a short walk or having a sedentary break by simply standing up from sitting after 45 mins). We do encourage them to undertake such light-intensity physical activity more often. In fact, light- physical activity behaviour is already part of normal daily life.

## **7. SAFETY REPORTING**

### **7.1 Temporary halt for reasons of subject safety**

In accordance to section 10, subsection 4, of the WMO, the sponsor will suspend the study if there is sufficient ground that continuation of the study will jeopardise the participant's health or safety. The sponsor will notify the accredited METC without undue delay of a temporary halt including the reason for such an action. The study will be suspended pending a further positive decision by the accredited METC. The investigator will take care that all subjects are kept informed.

### **7.2 AEs and SAEs**

#### **7.2.1 Adverse events (AEs)**

Adverse events are defined as any undesirable experience occurring to a subject during the study, whether or not considered related to trial procedure and the experimental intervention. All adverse events reported spontaneously by the subject or observed by the investigator or his staff will be recorded.

For the above purpose LiPAT will keep a digital AE-log which is accessible to the LiPAT investigational staff at all times. This AE-log will be checked daily and discussed at the weekly LiPAT clinical monitoring meeting. In addition, an internist is available for the investigational staff 24 hours a day to discuss any such AE.

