### **3. STUDY DESIGN**

This study is a single-blinded randomized controlled trial (enrollment via block randomization (block size of 4)). The duration of the study is 12 months; a 6-month intervention with a 6 month follow-up period to examine both the long-term health effects of the intervention as well as any long-term compliance to the intervention.

Study measurements of all participants will take place at baseline (month 1 (t = 0)), month 3 (t = 3), month 6 (t = 6), and month 12 (t = 12) at the Maastricht UMC+.

Participants in the intervention group will be instructed to increase their LiPA by decreasing sedentary time. Participants will follow 4 workshops in group sessions on strategies to change their behaviour and will receive a feedback physical activity monitor that will be worn continuously on the wrist and provide e-feedback on activity behaviour. During the COVID-19 crisis the workshops temporarily are offered online. The intervention procedures are described in more detail in section 5.

Participants in the control group will receive 4 workshops in group sessions on healthy lifestyle including information and strategies to increase LiPA and reduce sedentary time similar to the intervention group, but will not receive a feedback-activity monitor.

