Participants will be instructed to wear the activity monitor continuously, also during the night, to be able to monitor sleeping behaviour. Participants are advised only to take the device off when the battery has to be recharged. Data will be automatically transferred by Bluetooth to the mobile application and the protected cloud-based platform and internet interface so that the participant can monitor progress and, if so required additional e-feedback can be dispersed. If LiPA goals are met, participants will be automatically rewarded by means of positive (e-)reinforcement (e.g., by encouragement messages in the app ("Well done! You have met your LiPA goal!") and encouragement symbols (e.g., a smiley). There will be no negative messages dispersed to the participant if LiPA goals are not met. During the intervention, small (digital) prizes for encouragement (e.g. fruit basket or a digital "thumbs up") will be raffled among participants who reach their activity goals.

During the first month of the intervention, participants will get acquainted with the use of the Fitbit inspire and bi-weekly phone calls with participants are planned to monitor use of the feedback activity monitor and set LPA goals based on their habitual activity. After this run-in period, monthly phone calls with participants are planned during the second and third month to provide feedback on the Fitbit inspire use and to help participants to reach their LiPA goals with the use of the watch and web-based interface. As from month 4 onwards, no structural phone calls with participants are planned anymore and feedback rests entirely upon the digital platform as by choice of the participant. During the complete period of the intervention a manned help-desk is available for any questions by the LiPAT participants.

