### Control group

Participants in the control group are, like the intervention group, invited for 4 workshops. These workshops are similar to the workshops of the intervention group, yet without the Fitbit inspire device. During the workshops topics related to a healthy lifestyle are being introduced. This information is based upon general healthy lifestyle guidelines, exercise guidelines and diabetes guidelines. Participants in the control group will not receive the e-feedback monitoring device. During the complete period of the study a manned help-desk is available for any questions by the participants about LiPA.

For safety reasons, for both the intervention and control group, a medical doctor (internist) is available (24/7) to discuss / advise on any alterations in the use of glucose lowering medication for both participant and general practitioners (or diabetes nurse practitioners). It can be expected that the most enthusiastic participants will experience alterations in their glucose levels which may require adjustment of their medication. Daily clinical care however remains the responsibility of the participant's own diabetes care provider either being the general practitioner or the diabetes nurse practitioner.

To note: the activPal ® ([www.Paltech.plus.com](http://www.Paltech.plus.com)) and Fitbit inspire (<https://www.fitbit.com/inspire>) are both commercially available research and consumer products and are incorporated into the trial as measurement tools but are themselves not part of the research aims of the current project. Both the ActivPal ® and the Fitbit inspire will be purchased by the investigational team from the respective companies.

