### **6.2 Randomisation, blinding and treatment allocation**

Randomisation by the research staff will take place during the baseline visit (please see above) with / via block randomization in a block size of 4 (Suresh, KP. J Hum Reprod Sci. 2011).

Participants will be randomly assigned in Ldot, a web-based tool, designed to monitor study logistics, to the LPA intervention group or the control group.

Randomisation will be stratified according to sex to ensure an equal distribution of men and women in both groups.

This is a single-blind design. To ensure blinding, participants will be instructed to not discuss their assigned intervention during any of the trial visits with the research nurse or vascular technician performing any of the trial measurements.

The participants in the intervention group will be asked not to wear their Fitbit inspire device on trial visit days and will be reminded not to do so via the web interface.

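### Adverse events are collected passively while only the intervention arm is phoned in months 1–3, so non-serious events may be captured unequally, and no scheduled question covers glycaemic episodes between visits

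*Protocol*

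**What the plan says.** **Collection rule.** Protocol section 7.2.1 defines an adverse event broadly, then states: "All adverse events reported spontaneously by the subject or observed by the investigator or his staff will be recorded". The visit content in section 3.2 has no adverse-event item. The month-6 interview in section 6.1.3 concerns experience with the programme. The questionnaire about medical consequences in section 6.5 goes only to participants who have been withdrawn.

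**Contacts.** Section 3 gives every participant visits at baseline and months 3, 6 and 12. Section 5.1 says of workshops: "Participants in the control group are, like the intervention group, invited for 4 workshops". For the intervention arm it adds that in the first month "bi-weekly phone calls with participants are planned to monitor use of the feedback activity monitor", followed by monthly calls in months 2 and 3 and no structural calls from month 4. The control section plans no calls, and Table 1 lists phone feedback only under the intervention group.

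**Help-desk.** The intervention text says: "During the complete period of the intervention a manned help-desk is available for any questions by the LiPAT participants". The control text says: "During the complete period of the study a manned help-desk is available for any questions by the participants about LiPA".

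**Glucose.** Section 5.1 says: "It can be expected that the most enthusiastic participants will experience alterations in their glucose levels which may require adjustment of their medication". Section 3.2 schedules fasting glucose, HbA1c and an interview on medical history and medication at all four visits. Section 6.1.2 makes change in glucose-lowering medication an outcome. Section 6.3 adds an on-site fasting check with low and high flags. Section 6.3.1 withdraws participants if taking part leads to uncontrollable hypo- or hyperglycaemia.

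**Blinding.** Section 6.2 says "participants will be instructed to not discuss their assigned intervention during any of the trial visits with the research nurse or vascular technician" taking the measurements.

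**The concern.** When events are logged only if someone mentions or notices them, the count depends on how often participants and staff are in contact. Here one arm has more scheduled contact than the other, and all the extra contact falls in the first three months, when behaviour is being changed. Serious events would probably surface anyway. Minor falls, skin or foot complaints and mild hypoglycaemia may not.

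The second part concerns a harm that the protocol itself anticipates. Fasting readings and HbA1c three to six months apart describe glycaemic level. They do not show whether a participant had single episodes in between, yet the glycaemic withdrawal criterion needs such episodes to become known.

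At stake is whether the recorded events can be described by arm when the trial is used, as section 1 intends, to support a recommendation on light-intensity activity.

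**Working it through.** The plan states no figure on this point, so there is none to reproduce. The check is a count of contacts, followed by an illustration.

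**Step 1. Scheduled contacts after randomisation** (sections 3 and 5.1)

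- Visits, both arms: 3 (months 3, 6, 12).
- Workshops, both arms: 4 (months 1, 2, 3, 6).
- Calls, intervention arm only: 2 in month 1 if bi-weekly means every two weeks, plus 2 in months 2–3, giving 4. If it means twice a week, about 8 + 2 = 10.

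| Period | Intervention | Control | Ratio |
|---|---|---|---|
| Months 1–3 (1 visit, 3 workshops, 4 calls or none) | 1 + 3 + 4 = 8 | 1 + 3 = 4 | 2.0 |
| After month 3 (2 visits, 1 workshop) | 3 | 3 | 1.0 |
| Whole 12 months | 11 | 7 | 1.57 |
| Months 1–3, calls twice a week | 1 + 3 + 10 = 14 | 4 | 3.5 |
| Whole 12 months, calls twice a week | 17 | 7 | 2.43 |

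The imbalance lies entirely in months 1–3. The first workshop is also longer in the intervention arm (2 hours against 1), which the count ignores. The month-6 interview is planned for all participants, so it does not change the difference.

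**Step 2. What such an imbalance could do (illustration only)**

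Assume equal true risk in both arms and the same chance p of volunteering a problem at each of k contacts. The share recorded is 1 − (1 − p)^k. With k = 11 and k = 7:

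| Assumed p | Intervention | Control | Ratio |
|---|---|---|---|
| 0.05 | 43% | 30% | 1.43 |
| 0.10 | 69% | 52% | 1.32 |
| 0.20 | 91% | 79% | 1.16 |
| 0.30 | 98% | 92% | 1.07 |

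The documents give no value of p. The model treats a group session, a call and a clinic visit as equal chances to report, and lets a problem be mentioned at any of them. It overstates the effect for events arising after month 3, when scheduled contacts are equal. It also leaves out any influence in the other direction, such as reluctance to mention a device-related complaint at a blinded visit.

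**Step 3. Glucose coverage**

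The planned assessments after baseline are at months 3, 6 and 12, so the gaps are 3, 3 and 6 months. Section 8.1 allows that month-3 visits may be missing because of COVID-19; the gaps are then 6 and 6 months. Fasting glucose, HbA1c and medication use are covered in both arms at each visit that takes place. No section states a question on episodes since the last visit.

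**The case against.** The protocol plans no comparison of adverse-event rates between arms. Section 7 serves participant protection and reporting to the ethics committee, and extra reports from calls do no harm there. Both arms can reach an internist around the clock about glucose-lowering medication. The interview at each visit appears only as a heading and may in practice bring out episodes or falls. The help-desk difference may be loose drafting, and the desk is for questions, not event collection. All of this stands. It limits the weight of the point, but does not supply a common question or make counts from the stated rule comparable.

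Four stronger readings are tempting and are not supported:

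- **That the blinding instruction silences the intervention arm.** Section 6.2 addresses participants in both arms and covers their allocation, not complaints. Only the request to leave the Fitbit off on visit days is specific to one arm. The instruction might deter mention of a device- or activity-related problem, but that is conjecture.
- **That visits are the only contact the arms share.** Both also have four workshops and the internist.
- **That glucose problems are never looked for.** Glucose, HbA1c and medication use are assessed at every visit. The gap is confined to episodes between visits.
- **That the intervention arm will show an excess of events.** More calls push that way and reticence at visits could push the other way. The percentages above rest on assumed probabilities and establish neither direction nor size.

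**Conclusion.** The point holds as a weakness of safety ascertainment. The collection rule is passive and scheduled contact is unequal in months 1–3: 8 against 4, and 11 against 7 over the whole trial, on the every-two-weeks reading of bi-weekly. Unequal capture of non-serious events is a risk inferred from the design, not something the protocol states. Counts collected under this rule could not be interpreted by arm. Separately, glycaemic episodes between visits have no stated route into the record other than being volunteered or noticed, although the protocol anticipates glucose alterations and its withdrawal criterion relies on such episodes becoming known.

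The PWV analysis and the sample size are not touched. The change is worth making because it is cheap and improves on the stated rule, not because the trial's main result is in doubt.

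**What to change.** 1. Add the same short, fixed safety items to the self-completed questionnaires both arms already fill in at months 3, 6 and 12: hypo- or hyperglycaemic episodes, falls or injury, skin or foot problems, and unplanned care since the last visit. Have them handled by existing staff who do not perform the measurements, so that an answer does not unblind an assessor. The protocol does not identify these staff, so the amendment should.
2. Base any by-arm description of adverse events on these items. Continue to log everything else, and record the source of events first learned of in the intervention-arm calls so that they can be told apart.
3. State in section 6.2 that the instruction not to discuss allocation does not cover the reporting of complaints.
4. Reconcile the two help-desk statements in section 5.1, which give different periods for the two arms.

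The cost is a few questionnaire items, a minor amendment and more non-serious events to log. The COVID-19 text shows that the trial was already under way, so only visits after the amendment would be covered. The report should say from which date the items were in use.
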